8.1.1.3. Subgroup Analysis

The primary efficacy endpoint will be descriptively summarized by the following subgroups:

- Age (< 65 years or ≥ 65 years);
- Gender (male or female);
- Race (White or Caucasian; Black or African-American; Asian; Other). If the number of Asian subjects is less than 5 in any treatment group, they will be included with Other; subjects identifying with more than one racial group will also be treated as Other;
- Diabetes status (history of T2DM or not);
- Renal function (eGFR at screening ≥ 60 or not);
- Pre-treatment status (presently medicated for hypertension or not);
- Types of anti-hypertension medication used;
- Baseline 24-hour mean SBP status (SBP≤160 mm Hg or SBP>160 mm Hg);

Same summary and ANCOVA model will be presented as in section 8.1.1.1 for each level of the subgroup.

In addition, univariate and multivariate exploratory analyses will be conducted to assess potential baseline and diagnosis effect in controlling of hypertension. For univariate analysis, ANOVA with each subgroup factor, treatment, and interaction between subgroup factor and treatment will be performed. Statistically significant subgroup factors, judging by the type 3 test of the factor (P-value < 0.1), will be further explored in multivariate analyses. ANOVA with these subgroup factors and treatment will be implemented.

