**Figure 1. THR-1442-C-603 Study Design**

## 3.2 Rationale for Design and Control Group

### 3.2.1 Rationale for the Selected Study Design

Bexagliflozin exhibits diuretic and hypotensive effects in hypertensive diabetics. The diuretic effect is immediate and improvement in blood pressure is observed over the first 6 to 12 weeks of treatment. The antihypertensive effect persists for 96 weeks. The magnitude of the effect correlates with the baseline blood pressure but appears to be independent of the baseline hemoglobin A1c, a measure of glycemic control. The two studies of protocol THR-1442-C-603 are designed to explore whether bexagliflozin will reduce blood pressure in adults with essential hypertension regardless of diabetes status. In addition, the use of a single treatment population allows extended safety and effectiveness data to be collected.

Study 603A is planned to evaluate the bexagliflozin treatment effect on SBP after the full effect of bexagliflozin has been achieved. Subjects will be randomized 1:1 to receive bexagliflozin tablets, 20 mg, or bexagliflozin tablets, placebo, for 12 weeks. The primary endpoint is the placebo-corrected change from baseline in ABPM SBP.

Study 603B, a randomized withdrawal study, is intended to measure the persistence of the antihypertensive effect of bexagliflozin. Subjects will receive bexagliflozin tablets, 20 mg for 12 weeks followed by 1:1 randomization to bexagliflozin tablets, 20 mg or bexagliflozin tablets, placebo. The primary endpoint is the placebo-corrected change from week 12 to week 24 in the ABPM SBP.

Under the close monitoring detailed in this protocol, placebo is the appropriate control treatment in the subject populations studied during the two 12-week evaluation periods. In order to establish baseline blood pressure and to allow compliance with the dosing regimen to be monitored, participating subjects will have participated in a 2 week run-in period prior to randomization.

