8.1.1.1. Primary Efficacy Analysis

Let $\mu_{\text{Bexagliflozin}, 12}$ and $\mu_{\text{PBO}, 12}$ represent the mean changes from baseline in 24-hour ambulatory SBP at Week 12 for bexagliflozin and placebo arm, respectively. The following hypotheses will be tested:

$$H_0: \mu_{\text{Bexagliflozin}, 12} = \mu_{\text{PBO}, 12} \text{ versus } H_1: \mu_{\text{Bexagliflozin}, 12} \neq \mu_{\text{PBO}, 12}$$

To test this hypothesis, an analysis of covariance (ANCOVA) will be applied to analyze the mean change in 24-hour average ABPM SBP. The ANCOVA model will include terms for diabetes status (history of type 2 diabetes mellitus [T2DM] or not), renal function (eGFR at screening as continuous variable), pre-treatment status (presently medicated for hypertension or not), randomized treatment, and the baseline 24-hour mean SBP as fixed effect covariates. Change from baseline will be the dependent variable. Analysis will be conducted on ITT analysis set. The last ABPM SBP post baseline will be used for the analysis.

Descriptive statistics (n, mean, Q1, median, Q3, SD, minimum, and maximum) will be reported by treatment group, along with the least squares means, differences between LS means, a 2-sided 95% confidence interval (CI) for each difference, p-value from the model effects.

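### The 603A subgroup exploration selects factors on their main effect, leaves the fitted interaction unused, and does not adjust for continuous baseline SBP

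*SAP*

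**What the plan says.** SAP 8.1.1.3 (Subgroup Analysis, 603A) has two parts.

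- **Level by level.** Eight subgroup factors are listed, diabetes status among them. For these, "Same summary and ANCOVA model will be presented as in section 8.1.1.1 for each level of the subgroup". The model in SAP 8.1.1.1 contains "randomized treatment, and the baseline 24-hour mean SBP as fixed effect covariates", so these estimates are baseline-adjusted.
- **Exploratory models.** Their aim is "to assess potential baseline and diagnosis effect in controlling of hypertension". In the univariate step, "ANOVA with each subgroup factor, treatment, and interaction between subgroup factor and treatment will be performed". Factors then go forward "judging by the type 3 test of the factor (P-value < 0.1), will be further explored in multivariate analyses". In the last step, "ANOVA with these subgroup factors and treatment will be implemented".

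The interaction is thus fitted, but the selection rule looks at the factor. No interaction estimate or p-value is named for reporting, and the multivariate model names no interaction. Continuous baseline 24-hour SBP is in neither ANOVA. It appears only as the candidate "Baseline 24-hour mean SBP status", split at 160 mm Hg.

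For 603B, SAP 8.2.1.1 does differently. There the treatment interaction with response class is added to a model that already contains baseline SBP, its type 3 p-value is judged at 0.10, and LS means with CIs are given for each class and treatment.

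Protocol 3.2.1 describes the two studies as "designed to explore whether bexagliflozin will reduce blood pressure in adults with essential hypertension regardless of diabetes status". It also says that the size of the effect is related to baseline blood pressure.

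**The concern.** A main effect says that a factor predicts the change in SBP, averaged over the two arms. An interaction says that the drug effect differs across levels of the factor. A subgroup section in a placebo-controlled trial is normally read for the second, yet the selection rule answers the first. Because 8.2.1.1 names the interaction when it means the interaction, the test of the factor in 8.1.1.3 is most naturally read as the main effect.

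Leaving out continuous baseline SBP adds a second problem. Change from baseline usually depends on baseline. A factor whose levels differ in baseline SBP can then look influential with no effect of its own, or a real effect can be cancelled.

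At stake are which factors reach the multivariate model, and whether the report contains a direct comparison of the drug effect between subjects with and without diabetes.

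**Working it through.** **Inputs.** SAP 3.7 gives 626 subjects at week 12 (313 per arm), an effect of 5 mm Hg and SD 15. The selection threshold is 0.1, so the critical value is 1.645. Factor prevalence p = 30% is the ceiling for diabetes in Protocol 3.2.3; 10% to 50% is the range shown. The sizes and patterns of factor effects are assumptions, because the documents give none.

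**The plan's own figure.** SE = 15 × √(2/313) = 1.199; z = 5/1.199 = 4.17; power = Φ(4.17 − 1.96) = 98.6%. This agrees with the stated >95%. The plan gives no operating figure for the selection step.

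**Selection step.** Let dP and dB be the factor's effect on change in the placebo and bexagliflozin arms.

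- Variance of the factor effect within one arm: v = 15² × [1/(313 × 0.3) + 1/(313 × 0.7)] = 225 × (1/93.9 + 1/219.1) = 3.423.
- Type 3 factor test: estimate (dP + dB)/2, SE = √(v/2) = 1.308.
- Interaction test: estimate dB − dP, SE = √(2v) = 2.617.
- Probability kept: Φ(|z| − 1.645) + Φ(−|z| − 1.645).

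The 5.7 mm Hg modification below is 9 − 3.3, that is, drug effects of 9 and 3.3 mm Hg. At 30% prevalence these average 0.3 × 9 + 0.7 × 3.3 = 5.0, the planned effect.

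| Pattern (dP, dB), mm Hg | z factor | Kept by SAP rule | z interaction | Kept on interaction |
|---|---|---|---|---|
| No effect (0, 0) | 0 | 10% | 0 | 10% |
| Prognostic (−4, −4) | 3.06 | 92% | 0 | 10% |
| Offsetting (+2.85, −2.85) | 0 | 10% | 2.18 | 70% |
| Partly offsetting (+1.5, −3.5) | 0.76 | 20% | 1.91 | 60% |
| Active arm only (0, −5.7) | 2.18 | 70% | 2.18 | 70% |
| Same direction (−2, −7.7) | 3.71 | 98% | 2.18 | 70% |

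The one-arm row is an identity: both the estimate and the SE of the interaction are twice those of the factor test. For prevalence 10% to 50%, the partly offsetting row runs 14% to 22% against 35% to 67%.

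**Omitting continuous baseline SBP.** Further assumptions: slope of change on baseline −0.5, baseline SD 10, p = 30%; 3,000 simulated trials per scenario.

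- A factor with no effect whose levels differ by 5 mm Hg at baseline shifts the change by −0.5 × 5 = −2.5 mm Hg in both arms. It is kept 59% of the time unadjusted and 10% adjusted. With a 3 mm Hg difference it is kept 30% and 10%.
- A modifier of −5 mm Hg in the active arm only has an average factor effect of −2.5. If its group starts 5 mm Hg lower, the baseline shift is +2.5 and the two cancel. The factor test keeps it 10% of the time unadjusted and 62% adjusted. The interaction test keeps it 59% and 64%.

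**Do the within-level ANCOVAs fill the gap?** Take an identical 5 mm Hg effect in both diabetes levels, SD 15, with no credit for covariates.

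- Diabetic: SE = 15 × √(2/93.9) = 2.189, z = 2.284, power 62.7%.
- Non-diabetic: SE = 15 × √(2/219.1) = 1.433, z = 3.489, power 93.7%.
- One level significant and the other not: 0.627 × 0.063 + 0.937 × 0.373 = 39%.

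Side-by-side p-values would therefore look inconsistent in about four trials in ten with no difference in effect.

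**The case against.** Much of the case on the other side stands.

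- **The interaction is in the plan.** A reader might infer that the treatment-by-diabetes interaction is never tested. The documents do not support that: it is a term in the univariate model for every factor. What is missing is an instruction to report or use it. The table shells are in a separate document and may print it.
- **The diabetes question is partly answered.** The protocol sentence can mean that the drug works in both groups, and the baseline-adjusted ANCOVAs show this by level. It is design rationale; no listed objective names a treatment-by-diabetes comparison. This stands, but those ANCOVAs do not test whether the effects differ.
- **Loss of modifiers is not general.** A reader might take the 10% against 70% contrast as typical. It needs exactly opposite effects in the two arms, which nothing in the documents suggests. A one-arm modifier fares the same under both rules, and one that shifts both arms in the same direction is kept more often by the SAP rule.
- **Baseline SBP is not wholly absent.** It is a candidate factor in two categories and a covariate in the within-level models. The figures for its omission rest on an assumed slope, SD and imbalance.
- **The aim can be read as prognostic.** On that reading, main-effect screening and an additive model are coherent, and keeping a prognostic factor is intended. The SAP should then say so. Adjustment for continuous baseline SBP would still be needed to separate a factor's own effect from that of baseline.

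**Conclusion.** The point holds as a limited weakness of an exploratory step. The 603A rule selects on prognosis averaged over arms, does not use or name for reporting the interaction it fits, and drops it from the multivariate model. With 313 per arm, SD 15 and 30% prevalence, a purely prognostic 4 mm Hg factor is kept about 92% of the time. A modifier is lost only when its arm effects offset (down to the 10% noise rate) or when an unadjusted baseline difference masks it. These sizes depend on assumed effect patterns and, for the baseline part, on the assumed slope of −0.5, baseline SD of 10 and differences of 3 to 5 mm Hg.

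The documents do not support the stronger conclusions that the diabetes question goes unexamined or that the rule generally discards effect modifiers. The primary test, alpha, sample size and within-level estimates are unaffected.

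**What to change.** In SAP 8.1.1.3, before unblinding:

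1. State whether the exploration is about prognosis, effect modification or both.
2. Add continuous baseline 24-hour mean SBP to the univariate and multivariate models.
3. Report the treatment-by-factor interaction for every factor, with estimate, 95% CI and p-value, and always for diabetes status whatever its p-value. This gives 603A an explicit interaction test, as 8.2.1.1 does for 603B.
4. Where the aim is effect modification, select on the interaction (P < 0.1) and carry the selected interactions into the multivariate model.

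The cost is a few lines of SAP text and table shells. No new data are needed, and the interaction terms are already fitted. The downside is limited power: about 60% for a 5 mm Hg interaction at 30% prevalence, and 35% at 10% prevalence. Multiplicity also remains: with eight null factors, one test each and independence, the chance of keeping at least one is 1 − 0.9⁸ = 57% under either rule. The results should stay labelled as exploratory.

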8.1.2. Secondary Efficacy Endpoints and Analyses

The secondary efficacy endpoints include mean ambulatory and seated office SBP, mean ambulatory and seated office DBP. Secondary efficacy endpoints will be accessed without multiplicity adjustment. Analyses will be primarily based on ITT analysis set.

8.1.2.1. The proportion of subjects who achieve a reduction of mean ambulatory SBP of 10 mm Hg or greater

Subjects who achieve a reduction of mean ambulatory SBP of ≥ 10 mm Hg will be summarized using frequency and percentage by treatment arm. Logistic regression will be used to analyze the treatment effect. The model will include diabetes status (history of T2DM or not), renal function (eGFR at screening as continuous variable), pre-treatment status (presently medicated for hypertension or not), baseline mean

ambulatory SBP value and randomized treatment. The LS Mean responding proportion and 95% CI will be estimated within each treatment group from a logistic regression model. A p-value for comparison by treatment group will also be provided. Two different outcomes will be explored:

- Responder will be defined using the last-post baseline value. If a subject received rescue medication, the value prior to the initiation of rescue medication will be used (primary analysis);
- Subjects with no post baseline assessments prior to early withdrawal from the study or initiation of the rescue medication will be considered as non-responders (sensitivity analysis).

8.1.2.2. The proportion of subjects who achieve ambulatory SBP of 135 mm Hg or less

The summary and analyses will be provided as in section 8.1.2.1.

8.1.2.3. The placebo-adjusted change from baseline to week 12 in seated office SBP

A summary and ANCOVA model will be presented as in section 8.1.1.1. The model will use baseline seated office SBP in place of baseline mean ambulatory SBP.

8.1.2.4. The proportion of subjects who achieve a mean seated office SBP of 140 mm Hg or less at week 12

A summary and analysis will be presented as in section 8.1.2.1. The model will use baseline seated office SBP in place of baseline mean ambulatory SBP.

8.1.2.5. The placebo-adjusted change from baseline to week 12 in mean ambulatory DBP

A summary and ANCOVA model will be presented as in section 8.1.1.1. The model will use baseline mean ambulatory DBP in place of baseline mean ambulatory SBP.

8.1.2.6. The proportion of subjects who achieve a mean ambulatory DBP of 87 mm Hg or less at week 12

A summary and analysis will be presented as in section 8.1.2.1. The model will use baseline mean ambulatory DBP in place of baseline mean ambulatory SBP.

8.1.2.7. The proportion of subjects who achieve a mean ambulatory DBP of 4 mm Hg or greater

A summary and analysis will be presented as in section 8.1.2.1. The model will use baseline mean ambulatory DBP in place of baseline mean ambulatory SBP.

8.1.2.8. The placebo-adjusted change from baseline to week 12 in seated office DBP

A summary and ANCOVA model will be presented as in section 8.1.1.1. The model will use baseline seated office DBP in place of baseline mean ambulatory SBP.

8.1.2.9. The proportion of subjects who achieve a mean seated office DBP of 90 mm Hg or less at week 12

A summary and logistic model will be presented as in section 8.1.2.1. The model will use baseline seated office DBP in place of baseline mean ambulatory SBP.

8.1.2.10. The trough-to-peak ratio of ABPM SBP at week 12

Trough/Peak ratio will be calculated based on the four valid measurements centered on approximate T_{max} (4 h post-dose, i.e. 2 measurements on or before 4 h and 2 measurements after 4 h) and the four valid measurements immediately preceding the removal of the monitor and prior to administering a tablet. The ratio will be summarized by treatment arm at week 12. The first 24-hour hourly change from baseline since dose administration will be summarized by treatment group and time (i.e., 0h post-dose, 2h post-dose, ..., and 23h post-dose). Hour 0 will be the hour when dosing is occurred. All measures at 0h post-dose are measures within the same clock hour, but after dosing.

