### Secondary Objectives of Study 603A

Additional effectiveness outcomes will be assessed from ambulatory as well as seated office blood pressure measurements.

Secondary endpoints based on mean ambulatory SBP will include the proportion of subjects who achieve a reduction of mean ambulatory SBP of 10 mm Hg or greater and the proportion of subjects who achieve a mean ambulatory SBP of 135 mm Hg or less at week 12.

Secondary endpoints based on seated office SBP will include the placebo-adjusted change from baseline to week 12 in seated office SBP and the proportion of subjects who achieve a mean seated office SBP of 140 mm Hg or less at week 12.

Secondary endpoints based on mean ambulatory DBP will include: the placebo-adjusted change in mean ambulatory DBP from baseline to week 12; the proportion of subjects who achieve a mean ambulatory DBP of 87 mm Hg or less at week 12; and the proportion of subjects who achieve a reduction of mean ambulatory DBP of 4 mm Hg or greater at week 12.

Secondary endpoints based on seated office DBP will include the placebo-adjusted change from baseline to week 12 in seated office DBP and the proportion of subjects who achieve a mean seated office DBP of 90 mm Hg or less at week 12.

An additional objective of study 603A will be an assessment of the maximum and minimum treatment effect (peak-trough ratio) by ABPM SBP at week 12.

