### **Study 603A**

Approximately 680 male or female adult subjects who exhibit an office seated blood pressure  $\geq 140$  mm Hg and  $< 180$  mm Hg, and who are taking no more than 4 anti-hypertension medications will be enrolled in study 603A. In the desired population,  $> 10\%$  of the subjects will have a baseline ABPM  $> 160$  mm Hg and  $< 30\%$  of the subjects will have type 2 diabetes

mellitus.

Subjects who meet the eligibility criteria at the screening visit (visit 1) will start a 2 week run-in period. At the end of the run-in period, subjects who have not been disqualified by laboratory testing results based on samples drawn at the screening visit, who have been compliant in taking the run-in medication, and who exhibit a seated SBP  $\geq$  140 mm Hg and  $<$  180 mm Hg will be eligible for participation. At the investigative site the subjects will take the last dose of run-in drug, will be fitted with an ABPM device and will start a 24-h ambulatory blood pressure monitoring (ABPM) to establish the baseline ABPM SBP and DBP. On the following day, qualified subjects who have completed the 24-h ABPM with a mean 24-h SBP  $\geq$  135 mm Hg will be randomly assigned to receive bexagliflozin tablets, 20 mg or placebo, using an interactive web response system (IWRS). If  $<$  64 SBP readings are recorded, the ABPM must be repeated within 2 days. Prior to randomization, subjects who cannot successfully complete the ABPM within two attempts will be considered screen failures.

Randomization will be stratified according to diabetes status (history of T2DM or not), renal function (eGFR  $\geq$  60 or not), presently medicated for hypertension or not, and ABPM SBP ( $<$  160 mm Hg or not).

A bottle of double blind study drug will be dispensed to each randomized subject with an instruction to take one tablet daily in the morning with a glass of water before or after breakfast. It will be recommended that subjects take the study drug at about the same time every day except on the days of scheduled site visit when the study drug will be administered at the investigational site.

A six week visit to the investigational site will allow seated office measures of systolic and diastolic blood pressure to be recorded.

At week 12 (end of study), the subject will visit the investigational site, consume the final tablet, and be fitted for ABPM.

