#### 6.11.5 Trough/Peak Ratio

Trough/Peak ratio will be calculated based on the four valid measurements centered on approximate  $T_{max}$  (4 h post-dose) and the four valid measurements immediately preceding the removal of the monitor and prior to administering a tablet.

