## 9.6 Secondary Efficacy Endpoints

Secondary efficacy endpoints will be accessed without multiplicity adjustment. Analyses will be primarily based on ITT analysis sets.

Absolute values and changes from baseline (Day 1 for study 603A or Week 12 value for study 603B) in vital signs measurements, pulse pressure, body weight, peak-trough ratio of ABPM SBP, and HbA1c will be summarized descriptively. Mean treatment effects will be estimated based on ANCOVA using similar method as described for the primary endpoint.

The responder assessments, such as the proportion of subjects who achieve specific goals, will be summarized by frequency table; logistic regression will be used to analyze the treatment effect with 95% CIs for the fraction responding within each treatment group and between treatment groups. Analyses will be based on all observed assessments prior to rescue medication or study end. In addition, a sensitivity analysis by assuming non-responder for subjects who had no post baseline assessments prior to early withdrawal of the study or initiation of the rescue medication, will also be performed.

In addition, changes in mean ambulatory SBP/DBP or office seated SBP/DBP after 12, 24, or 36 weeks of bexagliflozin treatment will also be summarized using combined 603A and 603B evaluations.

Detailed analyses will be defined in the statistical analysis plan.

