3.1.2. Secondary Objectives

Secondary objectives based on mean ambulatory SBP:

- The proportion of subjects who achieve a reduction of mean ambulatory SBP of 10 mm Hg or greater;
- The proportion of subjects who achieve a mean ambulatory SBP of 135 mm Hg or less at week 12;
- The maximum and minimum treatment effect (trough-to-peak ratio) by Ambulatory blood pressure monitoring (ABPM) SBP at week 12.

Secondary objectives based on seated office SBP:

- The placebo-adjusted change from baseline to week 12 in seated office SBP;
- The proportion of subjects who achieve a mean seated office SBP of 140 mm Hg or less at week 12.

Secondary objectives based on mean ambulatory diastolic blood pressure (DBP):

- The placebo-adjusted change in mean ambulatory DBP from baseline to week 12;
- The proportion of subjects who achieve a mean ambulatory DBP of 87 mm Hg or less at week 12;
- The proportion of subjects who achieve a reduction of mean ambulatory DBP of 4 mm Hg or greater at week 12.

Secondary endpoints based on seated office DBP

- The placebo-adjusted change from baseline to week 12 in seated office DBP;
- The proportion of subjects who achieve a mean seated office DBP of 90 mm Hg or less at week 12.

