4.1.2. Secondary Efficacy Endpoints

- The proportion of subjects who achieve a reduction of mean ambulatory SBP of 10 mm Hg or greater;
- The proportion of subjects who achieve a mean ambulatory SBP of 135 mm Hg or less;
- The trough-to-peak ratio of ambulatory SBP at week 12;
- The placebo-adjusted change from baseline to week 12 in seated office SBP;
- The proportion of subjects who achieve a mean seated office SBP of 140 mm Hg or less at week 12;
- The placebo-adjusted change in mean ambulatory DBP from baseline to week 12;
- The proportion of subjects who achieve a mean ambulatory DBP of 87 mm Hg or less at week 12;
- The proportion of subjects who achieve a reduction of mean ambulatory DBP of 4 mm Hg or greater;
- The placebo-adjusted change from baseline to week 12 in seated office DBP;
- The proportion of subjects who achieve a mean seated office DBP of 90 mm Hg or less at week 12;

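### As literally written, the trough/peak ratio uses measured week-12 pressures with no baseline or placebo subtraction, although its objective is a ratio of treatment effects

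*SAP*

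**What the plan says.** **Objective.** Protocol 2.1 and the Synopsis plan an "assessment of the maximum and minimum treatment effect (peak-trough ratio) by ABPM SBP at week 12". SAP 3.1.2 lists "The maximum and minimum treatment effect (trough-to-peak ratio) by Ambulatory blood pressure monitoring (ABPM) SBP at week 12". SAP 4.1.2 then makes "The trough-to-peak ratio of ambulatory SBP at week 12" a secondary efficacy endpoint.

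**Calculation.** Protocol 6.11.5 and SAP 8.1.2.10 give the same inputs: four valid readings centred on about 4 h post-dose, and "the four valid measurements immediately preceding the removal of the monitor and prior to administering a tablet". The SAP wording continues "prior to administering a tablet. The ratio will be summarized by treatment arm at week 12".

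**Adjacent summary.** SAP 8.1.2.10 goes on: "The first 24-hour hourly change from baseline since dose administration will be summarized by treatment group and time". Nothing connects this hourly table to the ratio.

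**Protocol 9.6.** Absolute values and changes from baseline in several variables, among them the "peak-trough ratio of ABPM SBP, and HbA1c will be summarized descriptively". The same paragraph calls for ANCOVA estimates of mean treatment effects. SAP 8.1.2.10 gives no ANCOVA for the ratio, and SAP section 12 (changes from the protocol) does not mention the ratio.

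**The concern.** In a placebo-controlled trial a treatment effect is a between-arm difference, here in change from baseline. A trough-to-peak ratio of effects has a clear scale: 1 means the effect at peak is fully present at trough, and 0 means none is left. A ratio of two measured pressures within one arm lacks that scale. It is close to 1 in any arm, it carries the day's blood pressure rhythm, and it goes up when the trough effect is lost.

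The SAP writes subtraction where it wants it. The neighbouring continuous endpoints in SAP 4.1.2 are placebo-adjusted changes, each with an ANCOVA in section 8.1.2. The ratio has neither.

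What is at stake is the evidence on duration of effect over the dosing interval, which matters for a once-daily tablet. A value near 1 would be taken as full effect at trough, yet placebo also gives about 1. A higher value on bexagliflozin would look favourable and mean the opposite.

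**Working it through.** The documents give no numerical value for the ratio, so there is no planned figure to reproduce. The check compares the literal rule with a ratio of effects.

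**Inputs**
- From the documents: planned 603A effect 5 mm Hg and SD of change in 24-h mean SBP 15 mm Hg (SAP 3.7); 626 subjects at the end of 603A, so 626/2 = 313 per arm.
- Assumed: SBP S = 135, 150 or 179 mm Hg; peak effect P = 4, 5 or 7 mm Hg; a clock-time difference c between the trough and peak windows of −8, 0 or +8 mm Hg, shared by both arms; fraction f of the peak effect remaining at trough = 1, 0.5 or 0.

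**1. Literal ratio**

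Placebo = (S + c)/S. Bexagliflozin = (S + c − fP)/(S − P).

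At S = 150, P = 5, c = 0 the placebo ratio is 1.000:
- f = 1: 145/145 = 1.000, contrast 0.000
- f = 0.5: 147.5/145 = 1.017, contrast 0.017
- f = 0: 150/145 = 1.034, contrast 0.034

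Over the whole grid:

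| Effect kept at trough | Ratio of effects | Literal ratio, bexagliflozin minus placebo |
|---|---|---|
| 100% | 1 | −0.003 to +0.003 |
| 50% | 0.5 | +0.010 to +0.031 |
| 0% | 0 | +0.022 to +0.058 |

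The clock-time term nearly cancels between arms but not within an arm. At f = 0 the bexagliflozin ratio runs from 0.97 to 1.12. With a 3 mm Hg placebo fall and a peak-time baseline of 150, a trough-time baseline of 140 or 160 gives a placebo ratio of 137/147 = 0.932 or 157/147 = 1.068. That shift is larger than any drug effect in the table.

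**2. Would the literal contrast be detectable?** Simulated subjects with mean SBP 150, between-subject SD 12 and independent window SD 8 give an SE of about 0.006 at 313 per arm (0.005 to 0.009 for window SD 6 to 12). Complete loss at trough (0.034) would be seen, but as a higher ratio.

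**3. Other readings of the text**
- *Per-subject ratio of changes.* The share of subjects with a peak change at or above zero is Φ(−m/15) for a mean fall m: 37% at 5 mm Hg, 30% at 8 and 21% at 12. Such ratios are unstable.
- *Ratio of within-arm mean changes.* With an assumed 3 mm Hg placebo-arm fall and a 5 mm Hg peak effect, complete loss at trough gives (3 + 0)/(3 + 5) = 0.375 where the effect ratio is 0.

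**4. Arm-level ratio of placebo-subtracted changes.** SE of each difference = SD × √(2/313): 1.20 at SD 15 and 1.44 at SD 18. Fieller 95% intervals with a peak effect of 5:

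| SD, correlation | True ratio 1 | True ratio 0 |
|---|---|---|
| 15, 0.3 | 0.54 to 1.86 | −0.62 to 0.45 |
| 15, 0.6 | 0.62 to 1.60 | −0.73 to 0.39 |
| 18, 0.3 | 0.45 to 2.20 | −0.84 to 0.56 |

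The 15 mm Hg is for a 24-h mean. A four-reading window is probably noisier, hence the SD 18 row, where the two intervals overlap slightly.

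**The case against.** The strongest reply is that the text is silent rather than wrong. It names the readings the ratio is based on and gives no formula; the objective speaks of treatment effect; the SAP defines how changes are computed at the start of section 8; and the next sentence in 8.1.2.10 uses change from baseline. The table shells are in a separate document and may state the formula. It is fair that subtraction is not expressly excluded, so the finding concerns the literal reading. But no sentence links a change or a placebo comparison to the ratio, and the other readings either divide by unstable denominators or still omit placebo.

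Protocol 9.6 does not close the gap. On the literal rule, a change from baseline or an ANCOVA of the ratio gives a difference of pressure ratios, not a ratio of effects.

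The hourly change table by arm is a real mitigation: a reader could form placebo-subtracted effects near 4 h and 23 h from it. It does not define the listed endpoint. It is also fair that SAP 8.1.2.10 plans no test of the ratio, that the Protocol calls it an additional objective and omits it from the Synopsis list of secondary assessments, and that the corrected ratio will be imprecise. These points limit the importance of the finding without removing it.

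**Conclusion.** The concern holds. Followed as written, SAP 8.1.2.10 and Protocol 6.11.5 produce a quantity that does not measure the stated objective and moves in the wrong direction: bexagliflozin minus placebo is within 0.003 of zero when the effect lasts fully, and +0.022 to +0.058 when it is lost at trough. The sizes rest on the assumed SBP range, peak effect and clock-time difference. The direction does not depend on the values chosen within that grid. The scope is one secondary endpoint without multiplicity adjustment; the primary analysis is unaffected. It should be corrected, with medium confidence, because the text leaves the subtraction unstated rather than ruling it out.

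**What to change.** In SAP 8.1.2.10, replace the within-arm ratio summary with one arm-level ratio: the bexagliflozin-minus-placebo mean change from baseline in the trough window, divided by the same difference in the peak window, with a Fieller or bootstrap 95% CI. Use matched post-dose windows of the baseline and week-12 recordings. Keep the hourly change-from-baseline table beside it.

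The paragraph should also state:
- how windows are matched when removal times or valid readings differ between the two recordings;
- whether the mean changes are covariate-adjusted;
- how the pre-rescue and carry-forward rule of SAP 8.1 applies to the windows.

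Record in SAP section 12 that this supersedes the change-from-baseline and ANCOVA treatment of the ratio in Protocol 9.6.

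The cost is one SAP paragraph, one section 12 entry and a short program. No new data are needed. At baseline "the subjects will take the last dose of run-in drug, will be fitted with an ABPM device", and Protocol 6.11.1 has the device start recording right after the dose, so both recordings can be aligned on time since dosing.
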